Biopsy for Histology	A (This can be the same biopsy as A under white light or it can be a new biopsy D)	С	B (This can be the same biopsy as B under white light or it can be a new biopsy E)	
Fluorescence Intensity by Neurosurgeon	X	X	X	
Tumor Content of Sample	X	Х	X	
Specimen Labeled	X	X	X	
Estimate made of extent	X	X	X	

IRB NUMBER: 12-135

of Fluorescent		
Tissue/Tumor Resected		

Specimens will be collected regardless of fluorescence.

Areas where biopsies have been made of fluorescent and non-fluorescent tissue within the tumor cavity will be graded by the neurosurgeon at the time of biopsy as 0 to +++ (3+) fluorescence. This will be recorded in the operating room each specimen identified with a code. The pathologist who reviews each specimen will be blinded as to the extent of fluorescence in the area where the biopsy was obtained.

Grade	Definition	
0	No fluorescence. No difference between any of the tissues visualized.	No fluorescence
+	Low fluorescence. Red glow is barely distigushed from surrounding non-fluorescent tissue.	Weak fluorescence
++	Moderate fluorescence. Dull red glow of fluorescent tissue.	
+++	High fluorescence. Bright red glow of fluorescent tissue	Strong fluorescence

The neurosurgeon is responsible for:

- An overall assessment of the detection of tumor within the cavity provided by the fluorescence imaging.
- Judging the extent of resection of the tumor or fluorescent tissue.
- Under white light:
 - Identifying at least one area of obvious tumor and biopsying that site.
 Then switch to blue light and grading the fluorescence at the site.
 - Identifying at least one area of obviously normal (but possibly edematous) brain in the wall of the tumor resection cavity in an area of non-eloquent brain and biopsying that site. Then switch to blue light and grading the fluorescence at the site.
- Under blue light:
 - Identifying at least one fluorescent area within the tumor cavity in an area of non-eloquent brain and biopsying and grading that site's fluorescence.
 It may not be necessary to biopsy this area if this same area has already been biopsied under white light.
 - Identifying at least one non-fluorescent area within the tumor cavity in an area of non-eloquent brain and biopsying and grading that site's fluorescence. It may not be necessary to biopsy this area if this same area has already been biopsied under white light.

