8. CORRELATIVE/SPECIAL STUDIES

- 8.1 Assessment of Visual Tumor Discrimination
 - 8.1.1 Overall assessment of Tumor Discrimination With the tumor and tumor cavity exposed, the neurosurgeon will visualize the tumor and tumor cavity under white light and again under deep blue light illumination and assess the ability of fluorescent illumination to distinguish tumor from normal brain tissue. This subjective assessment will be graded by the neurosurgeon at the time of visualization from 0 to +++ (3+).

Grade	Definition	
0	No fluorescence. No difference between any of the tissues visualized.	No fluorescence
+	Low fluorescence. Red glow is barely distigushed from surrounding non-fluorescent tissue.	Weak fluorescence
++	Moderate fluorescence. Dull red glow of fluorescent tissue.	
+++	High fluorescence. Bright red glow of fluorescent tissue	Strong fluorescence

- 8.1.2 Surgical Assessment of Fluorescence in Biopsy Specimens:
 Each biopsy specimen taken for this trial under blue light will be graded for fluorescence intensity at the time of biopsy by the neurosurgeon on a scale of 0 to +++ (3+).
- 8.1.3 Pathologic Assessment of Biopsy Specimens:
 All biopsy specimens, including those taken from the bulk tumor, will be reviewed by a neuropathologist.

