12. STATISTICAL CONSIDERATIONS

- 12.1 Study Design/Primary Endpoints
 - 12.1.1 Establish a safe dose for oral 5-ALA administration NCI Common Toxicity Criteria will be used to quantify toxicity following 5-ALA administration. Special attention will be paid to rash, pruritis, hepatic transaminitis, nausea and vomiting. Based on previously reported German trial, a 30 mg/kg dose is anticipated to be as well-tolerated as 10 and 20 mg/kg doses.
 - 12.1.2 Determine the sensitivity and specificity of the Phase 1 recommended dose in discriminating between normal and malignant tissue intraoperatively.

Four methods are being employed to assess discrimination of tumor from normal brain tissue.

- The neurosurgeon will assess the ability to distinguish tumor from normal brain tissue under ultraviolet illumination and grade the discrimination from 0 to +++ (3+) (See Section 8.1.1). Although arguably the most relevant measure, this is also the most biased and difficult to corroborate measure.
- Under white light the neurosurgeon will assess and biopsy an area of obvious tumor and an area of obviously normal (but possibly edematous) non-eloquent brain. The neurosurgeon will then assess whether these

IRB NUMBER: 12-135

- areas correspond to areas of strong, weak or no fluorescence seen under blue light.
- Under blue light, the neurosurgeon will assess the areas of fluorescence in the tumor cavity and will biopsy areas of strong fluorescence, weak fluorescence and no fluorescence. It may not be necessary to repeat some of these biopsies if the area has already been biopsied under white light. The pathologist will score tumor involvement in each biopsy specimen.

These data will be placed in the following grids – first a 3x3 grid as follows for an analysis of correlation, specifically a Cohen's kappa will be calculated to assess the strength of agreement between fluorescence and tumor density:

Fluorescence vs. Tumor Density	Solid Tumor	Infiltrating tumor/normal brain	No tumor (edematous peritumoral normal brain)
High Fluorescence	(Number of areas identified)	(Number of areas identified)	(Number of areas identified)
Weak Fluorescence	(Number of areas identified)	(Number of areas identified)	(Number of areas identified)
No Fluorescence	(Number of areas identified)	(Number of areas identified)	(Number of areas identified)

Second, these data will also be placed in a simpler 2x2 grid for fluorescence sensitivity/specificity analysis:

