APPENDIX B

Ultraviolet-Illuminated Operating Room Microscope

Tumor Dye Project – Technical Aspects

5-aminolevulinic acid (5-ALA) – a naturally occurring non-fluorescing metabolic precursor, induces synthesis of protoporphyin IX (PpIX). PpIX fluoresces when exposed to the excitation light of blue-violet (wavelength 375-400nm.) It gives off a light with characteristic peaks 635 and 704nm. This is best viewed by filtering (440 long pass filter) out most other wavelengths except a small amount of excitation light.

The excitation light source is a 400 W short-arc Xe-lamp and a short pass filter (440nm.) integrated into a standard Leica surgical microscope. This filter can be switched on or off by the surgeon when needed. Light is delivered through a commercially available liquid light guide. The Leica OH series microscope is modified so that these filters can be switched on and off whenever the surgeon wishes to observe the fluorescence.

Two special filters for the 5-ALA fluorescence are used in a standard Leica OH microscope. The filters are a short pass (<440nm) filter which rotates in front of the microscope's standard 400-watt Xe light source. In addition, a special long pass (>440nm) barrier filter in the optical path allows clear viewing of the red fluorescence. Both filters are inserted and removed with one button on the microscope handle. With the push of that one button, the standard Leica OH microscope can then go back to being the neurosurgical and spine microscope it was designed for.

Using these modifications intraoperative detection of tumor fluorescence is possible without disturbing the routine of the surgical procedure. Switching between the two illumination modes does not require significant surgeon optical accommodation and does not interrupt the operation. All of these modifications are readily made to the standard neurosurgical microscope and requires no additional personnel in the operating room.

Appendix	С
Eligibility	Checklist

ppendix C ligibility Checklist	

Clinical/Radiological evidence of a primary malignant brain tumor	
Age ≥ 18 years old	
ECOG Performance Status ≤ 2	
Karnofsky ≥ 60%	
Leukocytes ≥ 3,000/mcL	
Absolute neutrophil count ≥ 1,500/mcL	
Total bilirubin within normal institutional limits	
AST (SGOT)/ALT(SGPT) ≤ 2.5 X institutional upper limit of normal	
Creatinine within normal institutional limits	
or Creatinine clearance ≥60mL/min/1.73 m ²	
Not pregnant	
Able to understand and sign informed consent	

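### For the two white-light biopsies the plan grades fluorescence after the tissue is removed, so grade and histology can come from different tissue

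*Combined protocol and SAP*

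**What the plan says.** Section 4.1.2 lists the neurosurgeon's tasks. Under white light the first is "Identifying at least one area of obvious tumor and biopsying that site", followed by "Then switch to blue light and grading the fluorescence at the site". The same two-step instruction is given for the apparently normal site in the cavity wall.

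Section 12.1.2 keeps this order: "Under white light the neurosurgeon will assess and biopsy an area of obvious tumor" together with an area of normal brain, and then "The neurosurgeon will then assess whether these" areas correspond to strong, weak or absent fluorescence. The same section has the pathologist score tumor involvement in each biopsy specimen.

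Two other rules bear on grading. The general rule in section 4.1.2, which ties the grade to the moment of biopsy, reads "Areas where biopsies have been made of fluorescent and non-fluorescent tissue within the tumor cavity will be graded by the neurosurgeon at the time of" (the quote stops one word short of naming the procedure). Section 8.1.2 reads "Each biopsy specimen taken for this trial under blue light will be graded for fluorescence intensity at the time of biopsy".

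The operating-room table in section 4.1.2 allows the white-light specimens to be reused. For the strongly fluorescent sample it says "This can be the same biopsy as A under white light or it can be a new biopsy D"; the non-fluorescent sample has the parallel note for B and E.

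**The concern.** A sensitivity or specificity estimate needs the index test and the reference standard to be read on the same tissue. Here the index test is the fluorescence grade and the reference standard is histology. If the white-light specimen is taken out first and the site graded afterwards, the grade belongs to what remains and the histology to what was removed.

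The pairs concerned can feed a primary objective (1.1.2), through the kappa for fluorescence against tumor density and through the 2x2 grid. Those grids would then mix two procedures: blue-light sites, chosen by fluorescence seen before removal, and white-light sites, graded after it. The section 12.1.2 grid for white light is not affected in this way, because the white-light call is made on the intact site. Fluorescence and white light would therefore be set against histology on unequal terms.

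**Working it through.** The plan gives no figure on this point. Its one power statement (section 12.2: n = 34, kappa 0.490 against 0, two-sided 0.05, 80% power) is not an input. It is consistent with a large-sample null-variance calculation: ((1.960 + 0.842)/0.49)² = 32.7, so 33 patients, with 81.5% power at 34. The check below is mainly a reading of the text.

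**1. Order.** Sections 4.1.2 (both white-light sites) and 12.1.2 put the biopsy first and the blue-light look second. The order is stated, not left open.

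**2. What is scored.** The grade is of the site; the histology is of the specimen (section 12.1.2).

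**3. Does another rule repair it?** The general rule in section 4.1.2 ties grading to the time of biopsy but speaks of areas already biopsied; it does not place grading before removal. Section 8.1.2 attaches a grade to the specimen, but only for those taken under blue light. No rule has specimens A and B graded before removal or as excised pieces.

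**4. Route to the endpoint.** A and B may stand in for the strongly fluorescent and non-fluorescent samples, so their grade/histology pairs can enter both fluorescence grids.

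**5. Reach, at one specimen per category.**
- A and B reused, C added: 2/3 = 67% of a patient's specimens are graded after removal.
- D and E taken as new biopsies: 2/5 = 40%.

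These are shares of specimens whose grade could refer to other tissue. They are not shares of wrong grades.

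**6. Which grade changes matter.** Only grade 0 is labelled as no fluorescence, so + to +++ all count as fluorescent in the 2x2 grid, where sensitivity = a/(a+c) and specificity = d/(b+d).
- Tumor specimen, grade moves from +++ to +: it stays in cell a. Sensitivity is unchanged; only the 3x3 kappa can move.
- Tumor specimen, grade moves from + to 0: one count goes from a to c. The total a+c is fixed, so sensitivity falls by 1/(a+c). The reverse move raises it by the same amount.
- Tumor-free specimen, grade moves between 0 and +: one count passes between d and b. Specificity changes by 1/(b+d) in either direction.

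**7. Where bed and specimen could differ.** In the European phase II study summarized in section 2.3, mean tumor cellularity per patient was 79.1% in strongly and 30.78% in weakly fluorescing biopsies. Fluorescence thus follows local tumor content, and adjacent tissue with different content can have a different grade. Specimen A is taken from obvious tumor, where neighboring tissue is likely to be similar. Specimen B is taken from the cavity wall, where the lowest positive grade is by definition hard to tell from its surroundings. B is 1 of 3 or 1 of 5 specimens.

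**The case against.** The strongest reply is that the documents treat the area as the unit. The grids count areas, the grade is assigned to areas at the time of biopsy, and the biopsies are described as small. If the tissue around a small biopsy matches the piece removed, grading the area is valid. This stands as a limit on size: the mismatch is inferred from the order, and bed and specimen may often agree. It does not change the order, and nothing in the plan checks or records the agreement.

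The second reply is that the present order has a benefit. Taking the white-light biopsy before blue light keeps its placement free of influence from fluorescence, which protects the white-light grid. This stands, and any reordering has to preserve it.

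Third, a reader might take the treatment-day sheet in Appendix C as confirmation, since it lists the biopsy before the fluorescence grade. It is not: the rows run in the same order under blue light, so the layout says nothing specific about white-light sites. The wording for blue-light sites in section 4.1.2 also names biopsy before grading. Those sites differ because they are selected by fluorescence already seen, and section 8.1.2 grades the specimen.

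A reader might also infer that sensitivity is lowered by a known amount, or that 67% of grades are wrong. The documents support neither. They give no rate of disagreement between bed and specimen, and step 6 shows that a shift can go either way or leave the 2x2 grid untouched.

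**Conclusion.** The point holds as a defect in the measurement sequence for specimens A and B. Followed as written, the plan can pair a grade and a histology from different tissue, and these pairs can enter both fluorescence grids for objective 1.1.2. The reach is up to 2 of 3 or 2 of 5 specimens per patient, assuming one specimen per category and that A and B are entered in the grids as the plan allows.

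The size and direction of any bias cannot be derived from the documents. I expect it to be small in solid tumor and most relevant for B; that is judgment resting on tissue uniformity, not a calculation. Only shifts between grade 0 and any fluorescence affect sensitivity and specificity. The wording is certain and the effect is not, but the correction is cheap enough that it should be made.

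**What to change.** Amend sections 4.1.2, 8.1.2 and 12.1.2 so that they agree on one of two sequences for white-light specimens:

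- **Grade first.** Under white light, record the call (obvious tumor or obvious normal) and fix the exact biopsy point. Switch to blue light and grade that undisturbed point 0 to +++. Then biopsy the same point whatever the grade, as the plan's existing rule that specimens are collected irrespective of fluorescence already implies.
- **Biopsy first.** Keep the present order, but grade the excised specimen under blue light.

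In either case, record whether the undisturbed point or the excised specimen was graded, and extend section 8.1.2 to cover white-light specimens.

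The cost is amended wording and one added entry on the data sheet. In theatre it is a filter change: Appendix B notes that "Both filters are inserted and removed with one button on the microscope handle" and that switching does not hold up the operation. No extra biopsy, reader or patient is needed. The one downside belongs to the first option: seeing fluorescence before sampling could influence placement of the biopsy used in the white-light grid. The point must therefore be fixed beforehand; if that is not practicable, use the second option.

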4.1.3 Post-Operative Follow-up

Patients will be assessed for completeness of tumor resection within 24 hours following surgery using MRI both with and without gadolinium enhancement. A 24 post-surgical MRI within 24 hours of surgery is the standard of care for anyone undergoing surgical resection of a brain tumor. Subsequently, patients will be reimaged periodically to assess tumor progression according to the specific standard of care tumor treatment protocol determined by the Neuro-Oncologist. At these same intervals, when appropriate to the normal standard of care, routine liver function tests and physical examination will be performed.

4.1.4 Survival

Survival will be determined over two years from entry into the study by either periodic medical record review for patients seen in the SIU Neuro-Oncology Clinic, or by search of the Social Security Death Index (SSDI). Volumetric analysis will be performed with Tera-recon software on gadolinium contrast-enhanced T1W MRI to assess extent of resection (EOR) and residual tumor volume (RTV). These findings will then be correlated with progression free survival (PFS) and overall-survival (OS).

4.2 Definition of Dose-Limiting Toxicity

Dose-Limiting Toxicity (DLT) is determined by Adverse Events which are defined and graded following the CTEP, NCI Guidelines: Adverse Event Reporting Requirements of January 1, 2005

(http://ctep.cancer.gov/protocolDevelopment/electronic_applications/docs/newadverse_2 006.pdf) and the CTC/CTCAE Criteria. Expected Adverse Events (AE) have not been identified for 5-ALA by the NCI Comprehensive Adverse Event and Potential Risk list (CAEPR) but are identified in section 11.1.2 and 11.1.3 of this protocol. Those AEs which are determined to be Grade 2 or higher and directly attributed to 5-ALA or its metabolites will be considered to be dose-limiting for the purposes of determining dose escalation. At present, CTEP does not have a CAEPR or ASAEL for this agent (see Appendix D).

Since this study involves the one-time dose of the study drug, further dose modifications associated with the above adverse events will not be required.

4.2.1 Dose-Escalation Scheme

Dose escalation will proceed within each cohort according to the following scheme. Three subjects will be entered sequentially at each of the five dose levels (10, 20, 30, 40, and 50 mg/kg). This dose escalation scheme is more aggressive than standard accelerated dose escalation schemas published because we are already aware of safety data from Europe demonstrating no toxicity with oral doses of 50 mg/kg. An additional three subjects will be added to the recommended phase 2 dose level according to the following scheme. Three subjects are planned at each dose level in order to ensure that sufficient samples are available to determine fluorescent intensity differences between normal and malignant tissue at each dose level.

IRB NUMBER: 12-135

Each dose escalation will be approved by a Data Safety Monitoring Board determined by SCRIHS (see Section 11.5).

Dose Escalation and Modification Rule Table

# of Patients with DLT at a Given Dose Level	Escalation Decision Rule
0 out of 3	Enter 3 patients at the next dose level.
≥ 2 out of 3	Dose escalation will be stopped. This dose level will be declared the maximally administered dose (highest dose administered). Three (3) additional patients will be entered at the next lowest dose level if only 3 patients were treated previously at that dose.
1 out of 3	Enter at least 3 more patients at this dose level. - If 0 of these 3 patients experience DLT, proceed to the next dose level. - If 1 or more of this group suffer DLT, then dose escalation is stopped, and this dose is declared the maximally administered dose. Three (3) additional patients will be entered at the next lowest dose level if only 3 patients were treated previously at that dose.
<1 out of 6 at highest dose level below the maximally administered dose	This is generally the recommended phase 2 dose. At least 6 patients must be entered at the recommended phase 2 dose.

4.2.2 Phase 2 accrual of 16 additional subjects at the recommended phase 2 dose will commence once the phase 1 portion of this trial is completed. All correlative studies will be continued in the phase 2 portion of the study in order to define the differential fluorescence between normal and malignant brain tissue, enhancement of tumor resection, and survival impact of preoperative 5-ALA.

4.3 Supportive Care Guidelines

Patients will be managed by standard of care procedures for post-operative brain resection patients. In addition, patients will be sequestered in "low light" environment for 48 hours following the administration of 5-ALA.

Low light exposure conditions will start in the holding area immediately after ingestion of the study drug and will continue in all patient environments for at least 48 hours. These conditions include the following:

- Covering as much of the patient's skin, mucous membranes and eyes as possible
 except for those areas that need to be exposed for clinical care and evaluation (ie.
 placement of intravenous access, preparation for general anesthesia, preparation for
 surgery, observation during and after surgery, etc.). This will include the patient
 wearing dark glasses when awake.
- Windows in patient care areas will be covered and doors closed.
- Overhead room lights will be turned off in patient care areas. Lights that are necessary for patient care may be used at the minimal intensity required.
- Patient care areas do not need to be completely dark. Minimal light for patient, caregiver and visitor safety is allowed. Televisions, monitors and medical equipment may be used as necessary.

IRB NUMBER: 12-135

4.4 Duration of Therapy

A one-time, single-dose administration of oral 5-ALA 3 hours prior to induction of anesthesia for surgical resection of a malignant glioma is planned.

4.5 Duration of Follow-up

Patients will be followed for 2 years after surgery or until death, whichever comes first.

4.6 Criteria for Removal from Study

Because this study involves the one-time dose of the study drug followed by surgery, the only criteria for removal from the study would be if the patient either could not ingest the drug or could not undergo surgery.

5 DOSING DELAYS/DOSE MODIFICATIONS

One-time, single-dose administration of 5-ALA is planned, which precludes the need for intra-patient dose modification or delay.

